2.3 Sample size

Because we will target patients at higher risk of readmission, we hypothesize that the intervention could reduce the relative risk of readmission by 25%, i.e. more than the 18% reduction found in a recent meta-analysis where patients were mostly not at high risk for readmission. Based on previous findings, the expected 30-day readmission and death rate for patients at intermediate or high risk according to the simplified HOSPITAL score is around 27%. Allowing for 10% loss to follow-up, we determine that we will need 1,380 patients for the study to have 80% power, i.e. 690 in each arm.

The intervention phase (randomized controlled trial) will be restricted to the eligible patients who are at intermediate to high risk of 30-day readmission according to the simplified HOSPITAL score, i.e. $\geq 4/13$ points. We estimate to have around 18,000 patients discharged during the 20-month study period, 30% of which (5,400) will be at higher-risk for a 30-day readmission or death. This should be enough to reach the targeted sample size within the study time frame.

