2.7 Timing of outcome assessments

Table 1: Timing of outcome assessments

Assessment	Index hospitalization ¹⁾		Follow-up ²⁾ (post-discharge)		
	Pre-study screening	Screening (before inclusion)	Visit 1 (inclusion, day 0)	Visit 2 (day 3 ±1)	Visit 3 (day 14 ±1)
Demography	X				
Eligibility	X				
HOSPITAL score	X				
Informed consent		X			
Randomization		X			
Baseline characteristics		X			
Medical history		X			
Medication		X			
Activity of daily living (ADL Katz score)		X			
Exposition to intervention		X	X	X	
Medication discrepancy			X	X	
Adverse drug event			X	X	
Primary outcome: unplanned readmission or death					X
Secondary outcomes:					
Number of unplanned readmission					X
Number of days of hospitalization within 30 days					X
Diagnoses at readmission or cause of death					X
Number of emergency department visits					X
Number of PCP visits					X
Discharge satisfaction (3-CTM)					X
Costs of readmission					X

1) Assessment based on electronic health record and/or in person.

2) Assessment by phone call

CTU Bern	SAP for TARGET-READ phase 2	05.03.2019
	Version 1.0	Page 7 27

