6.1.2 Secondary outcomes

- Number of deaths within 30 days after discharge
- Number of patients with unplanned readmission within 30 days after discharge
- Time to first unplanned readmission or death within 30 days
- Main cause of readmission or death
- Post-discharge health care utilization within 30 days after discharge from index hospitalization:
 - number of unplanned hospital readmissions
 - number of planned hospital readmissions
 - total number of unplanned days of hospitalizations
 - total number of planned days of hospitalizations
 - number of emergency room visits
 - number primary care provider visits
- Patient's perspective (satisfaction) on quality of transition of care between hospital and home assessed by the three-item care transition measure (CTM-3) at 30 days
- Costs of readmission at 30 days

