6.2 Outcome derivation

Table 8: Derivation of primary and secondary outcomes.

Outcome	eCRF sheet	Variable	Variable type	Derivation	Outcome type
Primary: Unplanned readmission or death within 30 days after discharge	Baseline Characteristics	discharged_alive	Binary: No, Yes	discharged_alive==No or	Binary
	Follow-up calls	reas_pat_notre_d3, reas_pat_notre_d14	Categorical: Death, No answer, Other	reas_pat_notre_d3==Death or	
	Outcomes 30 days	death_d30	Binary: No, Yes	reas_pat_notre_d14==Death or	
Deaths within 30 days after discharge	Baseline Characteristics	unplanned	Integer: 0-6	death_d30==Yes or	Binary
		discharged_alive	Binary: No, Yes	unplanned>=1	
		reas_pat_notre_d3, reas_pat_notre_d14	Categorical: Death, No answer, Other	discharged_alive==No or	
Outcomes 30 days	Follow-up calls	death_d30	Binary: No, Yes	reas_pat_notre_d3==Death or	Binary
		reas_pat_notre_d14	Categorical: Death, No answer, Other	reas_pat_notre_d14==Death or	

Outcome	eCRF sheet	Variable	Variable type	Derivation	Outcome type
Unplanned readmission within 30 days after discharge	Outcomes 30 days	unplanned	Integer: 0-6	unplanned>=1	Binary
Time to first unplanned readmission or death	Baseline Characteristics	disch_date_index, baseline_death	Date: dmy	Time: min(30, min[baseline_death, date_death_d3, date_death_d14, date_death_d30 unplanned_in_1, lcontact_date] – disch_date_index)	Time-to-event
	Follow-up calls	date_death_d3, date_death_d14	Date: dmy		
	Outcomes 30 days	date_death_d30, unplanned_in_1	Date: dmy		
	End of Study	lcontact_date	Date: dmy	Failure: Primary==Yes	
Main cause of readmission or death	Follow-up calls	cause_death_d3, cause_death_d14	Free text	Tabulated free text fields will be manually categorized	Categorical
	Outcomes 30 days	dx_read30, cause_death_d30	Free text		
Number of unplanned hospital readmissions	Outcomes 30 days	unplanned	Integer: 0-6	-	Count
Number of planned hospital readmissions	Outcomes 30 days	planned_readmission	Integer: 0-8	-	Count
Total number of unplanned days of hospitalizations	Outcomes 30 days	unplanned_x_in, unplanned_x_out	Date: dmy	unplanned_x_out – unplanned_x_in	Count
Total number of planned days of hospitalizations	Outcomes 30 days	tot_rehosp_days_planned	Continuous: days	-	Count
Number of emergency room visits	Outcomes 30 days	nb_edvisits	Integer	-	Count
Number primary care provider visits	Outcomes 30 days	nb_pcpvisits	Integer	-	Count

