Offset for count variables	Baseline Characteristics	disch_date_index, baseline_death	Date: dmy	min(30, min[baseline_death, date_death_d3, date_death_d14, date_death_d30 lcontact_date] – disch_date_index)	Continuous
	Follow-up calls	date_death_d3, date_death_d14	Date: dmy		
	Outcomes 30 days	date_death_d30	Date: dmy		
	End of Study	lcontact_date	Date: dmy		
Patient's perspective (satisfaction) on quality of transition of care between hospital and home (CTM-3)	Outcomes 30 days	ctm1, ctm2, ctm3	Binary: No, Yes	ctm1==Yes & ctm2==Yes & ctm3==Yes	Binary
Costs of readmission	Costs at Outcomes 30 days	costs_30d	Continuous: CHF	-	Continuous

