6.3.1.2 Analysis of secondary outcomes

The number of patients that die will be compared between treatment groups using a Mantel-Haenszel risk difference with a two-sided 95% CI⁴ and a Cochran-Mantel-Haenszel test, both stratified for the stratification factors used in randomization.

The risk of 30 day unplanned readmissions in each group will be estimated using the cumulative incidence function with death as competing event calculated from flexible parametric survival models (e.g. using `stpm2` followed by `stpm2_standsurv` in Stata)^{5,6}. Groups will be compared using the cumulative incidence difference with 95% CI and a z-test, based on delta method standard errors and a normal approximation. We will also report the cumulative incidence of the competing event (death without readmission) for each group and the risk difference between groups.

Time to unplanned readmission or death will be graphically depicted by Kaplan-Meier curves for each treatment group. Groups will be compared using a log-rank test stratified for the stratification factors used in randomization. As an effect measure, we will use the restricted mean survival time truncated at 30 days calculated using flexible parametric survival models with the group and factors used at randomization as covariates⁷. The restricted mean survival time for each group and the difference between groups will be reported with 95% CI and a p-value.

The main cause of readmission or death will mainly be analyzed with descriptive statistics. The number and proportion of patients in each category will be shown for both groups.

Count outcomes (number of hospital readmissions, number of days of hospitalization, number of emergency room visits, number of primary care provider visits) will be presented with number of patients, person-time and incidence rate with 95% CI. Groups will be compared using a negative binomial regression with the group and the stratification factors as covariates and the observation time as offset. An incidence rate ratio with 95% CI and p-value will be reported. In case of an excess of zeros and overdispersion that cannot be modeled by the negative binomial distribution we will consider zero-inflated negative binomial regression (e.g. using function `zeroinfl` from R package `pscl`).

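### Total unplanned hospital days are derived without a cut at day 30, although the outcome and its person-time both stop at day 30

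*SAP*

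**What the plan says.** Section 6.1.2 lists "total number of unplanned days of hospitalizations" under "Post-discharge health care utilization within 30 days after discharge from index hospitalization". Table 1 (section 2.7) describes the assessment in the same way: "Number of days of hospitalization within 30 days". The window is therefore stated twice.

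Table 8 (section 6.2) derives the outcome from the entry and exit dates of each unplanned stay as "unplanned_x_out – unplanned_x_in" and adds nothing further. The same table defines the offset for all count outcomes as "min(30, min[baseline_death, date_death_d3, date_death_d14, date_death_d30 lcontact_date] – disch_date_index", so observation time ends at day 30, death or last contact, whichever comes first.

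Section 6.3.1.2 includes hospital days among the count outcomes ("number of days of hospitalization, number of emergency room visits, number of primary care provider visits"). It reports incidence rates with 95% confidence intervals for each group and then specifies the model: "Groups will be compared using a negative binomial regression with the group and the stratification factors as covariates and the observation time as offset".

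**The concern.** Numerator and denominator cover different periods. A stay that begins inside the window and ends after it contributes all its days to the count, while the person-time stops at day 30. A programmer who follows Table 8 literally will compute a different quantity from the one that section 6.1.2 defines.

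The omission does not look like house style. Table 8 writes an explicit minimum with 30 for time to first unplanned readmission or death, and again for the offset, but not for hospital days. Neither section 6.3 nor section 6.4 supplies the missing cut.

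At stake are the absolute rates of unplanned hospital days in both arms and, if the arms differ in when readmissions occur, the rate ratio between them.

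**Working it through.** **The plan's own figures.** The SAP gives no expected number of hospital days, so there is nothing to reproduce for this outcome. Its only computed design figure is the sample size. With 27% against 0.75 × 27% = 20.25%, two-sided 5% and 80% power, the normal approximation without continuity correction gives 621 per arm. Then 621 / 0.90 = 690 per arm, or 1,380 in total, as stated in section 2.3. That figure does not depend on hospital days.

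**Single stays** (days after index discharge, invented for illustration). As written: out − in. Cut: min(out, 30) − in.

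| In | Out | As written | Cut at day 30 |
|---|---|---|---|
| 10 | 20 | 10 | 10 |
| 25 | 45 | 20 | 5 |
| 29 | 50 | 21 | 1 |
| 2 | 40 | 38 | 28 |

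The last row gives 38 / 30 = 1.27 hospital days per day observed, which is impossible for a measure confined to the window. Cut, it is 28 / 30 = 0.93.

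**Average effect: inputs.**
- Control risk *p* = 0.27: section 2.3 expects a rate that "simplified HOSPITAL score is around 27"%. That rate is for readmission or death. It is used here as a readmission risk, which is a simplification.
- Intervention risk 0.2025: from the 25% relative reduction in section 2.3.
- Assumed, not in the SAP: at most one readmission per patient, exponential length of stay with mean *m* = 5, 7 or 10 days, the same in both arms, and 30 days of observation for everyone.

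**Formula.** A patient readmitted on day *t* is expected to spend m(1 − exp(−(30 − t)/m)) days inside the window, against *m* days uncut. With constant hazard λ = −ln(1 − p)/30, the share of counted days after day 30 is

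λ (exp(−30λ) − exp(−30/m)) / [p (1/m − λ)].

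In the control arm λ = 0.3147 / 30 = 0.01049. For *m* = 5: 0.01049 × (0.73 − 0.0025) / [0.27 × (0.2 − 0.01049)] = 0.149.

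The uncut rate ratio is 0.2025 / 0.27 = 0.75. The cut ratio is 0.75 × (1 − intervention share) / (1 − control share).

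| Mean stay (days) | Control share after day 30 | Intervention share, same timing | Ratio, cut | Intervention share, delayed | Ratio, cut |
|---|---|---|---|---|---|
| 5 | 0.149 | 0.154 | 0.746 | 0.190 | 0.71 |
| 7 | 0.210 | 0.216 | 0.745 | 0.259 | 0.70 |
| 10 | 0.295 | 0.301 | 0.744 | 0.350 | 0.69 |

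Same timing means constant hazard in both arms. Delayed means Weibull shape 1.3 in the intervention arm against 1.0 in the control arm, with the 30-day risks unchanged (numerical integration).

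The control-arm rate as written exceeds the windowed rate by a factor of 1 / (1 − share): 1.18, 1.27 and 1.42 for mean stays of 5, 7 and 10 days.

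**Sensitivity to timing.** If control-arm readmissions cluster early (Weibull shape 0.7), the shares fall to 11%, 16% and 24%. If readmission times are uniform over the 30 days, they are 17% for a mean stay of 5 days and 32% for 10 days.

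**The case against.** The strongest reply is that the treatment comparison is barely touched. With the same timing pattern in both arms, the ratio moves only from 0.75 to about 0.745. The larger shift, to between 0.71 and 0.69, needs an assumed delay for which the SAP gives no figure. This stands. A reader might infer that the planned comparison is materially biased, and the document does not support that. What survives is the error in the absolute rates, which section 6.3.1.2 also reports, and the direction of any distortion: if the intervention does delay readmission, the uncut count understates its benefit.

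A second reply is that the case report form may already restrict exit dates to day 30 or to the date of the 30-day assessment. That is possible, and the defect would then be smaller, but the SAP states no such rule. For the same reason, a reader should not infer that patients still in hospital at day 30 have no exit date, or that the longest stays are lost. The SAP does not say how an ongoing stay is recorded, and a short stay that begins on day 29 can be open at day 30 just as a long one can. This is a case for which a rule is needed, not a demonstrated loss of data.

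A third reply concerns planned days. They are taken from a single entered total, `tot_rehosp_days_planned`, and Table 8 shows no dates for them. It cannot be concluded that they are miscounted, and they cannot be truncated from the variables shown.

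**Conclusion.** The contradiction is in the text: the outcome and its offset stop at day 30, and the derivation of unplanned hospital days does not. Followed literally, Table 8 gives incidence rates that are too high in both arms. The excess days make up roughly 15% to 30% of those counted for mean stays of 5 to 10 days under a constant hazard, and fewer if readmissions come early. These percentages rest on assumed stay lengths and timing. The mismatch itself does not.

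The effect on the rate ratio is negligible with like timing and is towards 1 with delayed readmission in the intervention arm. The problem is confined to one secondary utilization outcome. The primary outcome, the time-to-event outcome, the readmission counts and the sample size are unaffected. It should be corrected before database lock.

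**What to change.** In Table 8, replace the derivation by a sum over all unplanned stays that start by the end of observation:

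min(`unplanned_x_out`, `disch_date_index` + offset time) − `unplanned_x_in`,

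where the offset time is the one already defined for the count outcomes (day 30, death or last contact, whichever is first). A cut at day 30 alone would not match the offset for patients who die or are last seen earlier. Add that a stay still open at the end of observation, or whose exit date is missing for that reason, is counted up to that end.

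For unplanned days this costs about one line of text and uses dates that Table 8 already lists. For planned days, only confirm and state that `tot_rehosp_days_planned` as entered is limited to the same 30 days.

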6.3 Analysis methods

6.3.1 Primary analysis

The primary analysis will be based on the FAS. Missing data will be handled according to section 6.4.

6.3.1.1 Analysis of the primary outcome

The proportion of patients that have an unplanned readmission or die will be calculated in both groups with a 95% Wilson score confidence interval. For the comparison between the two groups, a Mantel-Haenszel risk difference stratified for the stratification factors used in randomization (section 2.4) will be shown (transitional care – usual care). A two-sided 95% CI will be calculated according to the procedure described by Klingenberg⁴. A stratified Cochran-Mantel-Haenszel test will be used to test for differences (e.g. using `emh` in Stata).

6.3.1.2 Analysis of secondary outcomes

The number of patients that die will be compared between treatment groups using a Mantel-Haenszel risk difference with a two-sided 95% CI⁴ and a Cochran-Mantel-Haenszel test, both stratified for the stratification factors used in randomization.

The risk of 30 day unplanned readmissions in each group will be estimated using the cumulative incidence function with death as competing event calculated from flexible parametric survival models (e.g. using `stpm2` followed by `stpm2_standsurv` in Stata)^{5,6}. Groups will be compared using the cumulative incidence difference with 95% CI and a z-test, based on delta method standard errors and a normal approximation. We will also report the cumulative incidence of the competing event (death without readmission) for each group and the risk difference between groups.

Time to unplanned readmission or death will be graphically depicted by Kaplan-Meier curves for each treatment group. Groups will be compared using a log-rank test stratified for the stratification factors used in randomization. As an effect measure, we will use the restricted mean survival time truncated at 30 days calculated using flexible parametric survival models with the group and factors used at randomization as covariates⁷. The restricted mean survival time for each group and the difference between groups will be reported with 95% CI and a p-value.

The main cause of readmission or death will mainly be analyzed with descriptive statistics. The number and proportion of patients in each category will be shown for both groups.

Count outcomes (number of hospital readmissions, number of days of hospitalization, number of emergency room visits, number of primary care provider visits) will be presented with number of patients, person-time and incidence rate with 95% CI. Groups will be compared using a negative binomial regression with the group and the stratification factors as covariates and the observation time as offset. An incidence rate ratio with 95% CI and p-value will be reported. In case of an excess of zeros and overdispersion that cannot be modeled by the negative binomial distribution we will consider zero-inflated negative binomial regression (e.g. using function `zeroinfl` from R package `pscl`).

Each item of the CTM-3 score will be summarized by treatment group using relative and absolute frequencies. The number of patients with a yes on all items will be compared between treatment groups using a Mantel-Haenszel risk difference with a two-sided 95% CI⁴ and a Cochran-Mantel-Haenszel test, both stratified for the stratification factors used in randomization.

The costs of readmission will be analyzed by linear regression with the treatment group and the stratification factors used in randomization as covariates. The treatment effect will be presented as

CTU Bern	SAP for TARGET-READ phase 2	05.03.2019
	Version 1.0	Page 21 27

mean difference with 95% CI and a p-value. Model assumption will be checked visually using plots of residuals (residuals vs fitted values, QQ-plot). If model assumptions are violated, transformation of the outcome (e.g. log), more robust methods (e.g. robust standard errors or robust regression) or non-parametric methods (e.g. Wilcoxon-Mann-Whitney test or van Elteren's test) will be considered.

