4.2 Confidence intervals and p-values

A level of statistical significance of 5% will be used. All statistical testing will be two-sided. All tests will be accompanied by an effect measure (transitional care vs usual care) with a 95% confidence interval (95% CI).

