6.4 Missing data

The number of patients with non-missing observations will be reported for each outcome.

Missing data may occur due to drop-outs or deaths. The former will lead the absence of all outcome information as outcomes are only assessed once. Since the follow-up is very short we do not expect a lot of drop-outs and it is unlikely that these patients did have a readmission or died. Therefore, we will assume that drop-outs did not have a readmission and did not die. For survival analyses they will be censored at one day. For count outcomes they will be assumed to have no observed event and an offset of one day. For patient satisfaction multiple imputations will be used (section 6.4.1). If the amount of drop-outs is larger than 5%, we will do a sensitivity analysis in which the primary outcome (unplanned readmission or death) will be multiply imputed as a binary variable (section 6.4.1).

Death will not lead to missing data for the primary outcome, 30-day deaths and time to primary outcome. For 30-day unplanned readmission, death is a competing event and the cumulative incidence at 30 days will be used (section 6.3.1.2). Count outcomes will be handled by including the observation time as offset in the Poisson regression. For patient satisfaction multiple imputations will be used (section 6.4.1). In a sensitivity analysis, the worst possible outcome will be assigned to deaths (i.e. a negative respond to all question of the CTM-3).

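### For hospital days, the negative binomial error bars depend on a variance form the data need not follow, and SAP Section 6.4 calls the same analysis a Poisson regression

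*SAP*

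**What the plan says.** SAP Section 6.3.1.2 covers readmission counts, days of hospitalization, emergency visits and primary care visits in one sentence: "Groups will be compared using a negative binomial regression with the group and the stratification factors as covariates and the observation time as offset". The result is an incidence rate ratio with a 95% CI and p-value. The section does not say how the standard error is computed. It allows a zero-inflated negative binomial model to be considered if the negative binomial cannot accommodate the zeros and overdispersion.

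Section 6.4, on deaths, describes the same analysis differently: "Count outcomes will be handled by including the observation time as offset in the Poisson regression". Section 6.3.3 adds an exact Poisson test for counts as a crude sensitivity analysis.

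Section 6.1.2 defines health care utilization over the 30 days after discharge, and the offset in Table 8 (Section 6.2) is capped at 30 days. The Table 8 derivation of unplanned days, however, only subtracts each admission date from its discharge date and has no cut at day 30.

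On testing, Section 4.2 says "A level of statistical significance of 5% will be used" and "All statistical testing will be two-sided".

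**The concern.** A negative binomial model ties the variance to the mean through one dispersion parameter: variance = mu + alpha × mu². When about three quarters of patients have no hospital days, that parameter is set largely by the zeros. The model then implies a tail for the positive values, and real lengths of stay may be shorter or longer than that tail. The rate ratio itself is little affected, because it essentially compares mean days per unit of time. The CI and p-value are affected, because model-based standard errors take the implied variance at face value.

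Hospital utilization is a stated secondary objective (Section 1.2). If the error bars are too wide, a real reduction in days is missed more often than the data require. If they are too narrow, chance differences are declared significant too often. A Poisson model assumes a variance equal to the mean, which is far too small for days that arrive in blocks.

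**Working it through.** **1. The plan's own figure.** Section 2.3 assumes a 27% event rate and a 25% relative reduction, so 0.27 × 0.75 = 0.2025, with mean p̄ = 0.23625. With n = [1.96√(2p̄(1−p̄)) + 0.84√(p1(1−p1) + p2(1−p2))]² / (p1−p2)², n = 621 per arm. "Allowing for 10% loss to follow-up", 621/0.9 = 690, which agrees with "we will need 1,380 patients for the study to have 80% power, i.e. 690 in each arm". This covers the primary outcome only. The SAP gives no mean, SD, shape or power for hospital days.

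**2. Formulas (group-only model).** The estimate is the log ratio of arm means.
- Model-based SE = √Σ[1/(n·mu) + alpha/n]
- Robust SE = √Σ[s²/(n·mu²)]
- Approximate size at nominal 5% = 2[1 − Φ(1.96 × model SE / true SE)]

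**3. Poisson wording, by hand.** Assume 23.625% of patients have one stay, with mean 8 days and CV 0.6. The mean is 0.23625 × 8 = 1.89. The variance is 0.23625 × 64 × (1 + 0.36) − 1.89² = 20.56 − 3.57 = 17.0. The ratio is 17.0/1.89 = 9, so a Poisson SE is √(1/9) = one third of the true SE. Size = 2[1 − Φ(1.96/3)], about 51%.

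**4. Negative binomial, planned model.** Simulation with 1,380 patients; terms for group, risk stratum and four sites; log observation-time offset. Assumptions: an unplanned stay for 19% (intermediate risk) or 30% (high risk) of patients, mean 8 days per stay, 12% chance of a second stay, gamma or lognormal stays, 3,000 data sets per scenario. Power is for 25% fewer readmitted patients.

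| Days counted | CV of stay | Size, model-based | Size, robust | Power, model-based | Power, robust |
|---|---|---|---|---|---|
| Limited to 30-day window | 0.6-1.5 | 0.8-2.1% | 4.8-5.8% | 25-32% | 47-58% |
| No cut | 0.6 | 0.4% | 5.3-5.8% | 24% | 57-58% |
| No cut | 1.0 | 1.4-1.6% | 5.2-5.9% | 26-28% | 45-47% |
| No cut | 1.25 | 2.6-3.2% | 6.3-6.5% | 29-31% | 42% |
| No cut | 1.5 | 4.4-5.1% | 6.7-6.9% | 31-33% | 38-39% |
| No cut | 2.0 | 8.0-9.3% | 7.5% | 34-35% | 34-35% |

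Two rows checked against the formula:
- Window-limited gamma stay, CV 0.6: model SE 0.178, empirical 0.128. 1.96 × 0.178/0.128 = 2.73, so size is about 0.6%.
- No cut, CV 2: model SE 0.190, empirical 0.222. 1.96 × 0.190/0.222 = 1.68, so size is about 9%.

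A variant with 5% drop-outs (zero events, offset one day, as in Section 6.4), run for three window-limited distributions, changed little.

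**5. Group-only model at the plan's rates.** 690 per arm, 23.6% with a stay under the null, mean 8 days, days limited to the window. In seven of eight stay shapes, model-based size was 0.3-2.2%, and power at 27% against 20.25% was about 33-38% model-based and 42-67% robust. The eighth shape, gamma with CV 2, was near nominal. Robust size was 3-6%. Without a cut, the model-based test was nominal at CV 1.5 and ran at 9-11% at CV 2.

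**6. Planned days.** Assuming 5-10% of patients have a planned stay of mean 5 days (1,500 data sets per scenario), model-based size was 1.5-3.8% and robust size 5.9-9.5%.

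**7. Would the zero-inflated fallback intervene?** The fitted negative binomial predicted 75-77% zeros against 76.6% observed. The zeros alone would probably not trigger it.

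**The case against.** Negative binomial regression with an offset is a standard choice for counts. Section 6.3.1.2 does not prescribe model-based standard errors, and it has a fallback model. The trial is powered only for the primary outcome, and in many scenarios the error is conservative. All of this is true and limits the consequence. It does not settle the matter: where the SAP contemplates robust errors it names them (costs in Section 6.3.1.2, the Poisson subgroup model in Section 6.3.4), so silence here points to the default.

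A reader might infer that the planned intervals for hospital days are always too wide. The documents do not support that. They give no stay distribution, and Table 8 has no cut at day 30. Without a cut the direction reverses for heavy tails. In one check with uncut lognormal stays at CV 2, size was 8.8% and power was 34% model-based against 29% robust, so the power gain disappears as well.

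A reader might also infer that robust errors are a complete and costless repair for every count outcome. They are not. They run somewhat above 5% for rare planned stays and for uncut heavy tails, and readmission counts, emergency visits and primary care visits were not examined. Nor does the SAP say that each readmitted patient has one stay: the form allows up to six unplanned readmissions. The 27% covers readmission or death, so using it as a readmission rate is an assumption.

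**Conclusion.** The point holds conditionally. With default standard errors, the interval and test for hospital days depend on a variance form that zero-heavy length-of-stay data need not follow. For days limited to the outcome window, the likely error is conservatism (size mostly about 0.3-2%) with a material loss of power. If days beyond day 30 are counted, the error runs from conservative to anti-conservative (about 8-11% at CV 2). The mechanism is well supported. The sizes rest on assumed readmission shares, a mean stay of 8 days and assumed stay shapes.

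The conflict between Sections 6.3.1.2 and 6.4 needs no such assumptions. It is plain in the text and matters, since a Poisson fit with model-based errors could reject a true null about half the time in the example above. The primary outcome is not touched.

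**What to change.** - In Section 6.3.1.2, keep the log-link negative binomial model and the rate ratio, and state that CIs and p-values for hospital days use robust (sandwich) standard errors.
- In Table 8, limit counted days to the 30-day window, so that they match the definition in Section 6.1.2 and the capped offset.
- In Section 6.4, replace the Poisson wording with the model of Section 6.3.1.2.
- For planned days, add a bootstrap or permutation check, because robust errors alone can run at about 6-9% when stays are rare.

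The cost is one option in the code, a truncation rule in the derivation, one resampling check and short wording changes, with no new data collection. The price is that robust errors can be mildly anti-conservative for rare stays or very heavy tails. The window limit reduces the heavy-tail problem, and the resampling check addresses rare planned stays.
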